### 11.1.3 Safety and Tolerability Endpoints

The primary safety endpoints include the following:

• Incidence, frequency and severity of AEs, Serious AEs, treatment-related AEs (related to IMM-101 and/or nivolumab/ipilimumab (as applicable), immune-related AEs (as listed in the SmPC for nivolumab), Grade 3 and above AEs and AEs leading to IMM-101 discontinuation or study withdrawal throughout the study.

The secondary safety endpoints include the following:

- Incidence and frequency of laboratory parameter abnormalities
- Change from baseline values in laboratory parameter values
- Incidence and frequency of local injection site reactions.

Page 77 of 98

Exploratory safety endpoints include the following:

• For the subgroup of patients in cohort B who receive IMM-101 + ipilimumab as subsequent treatment: The incidence, frequency and severity of adverse events, serious adverse events, treatment-related adverse events and immune-related adverse events (as listed in the SmPC for ipilimumab) experienced following the start of ipilimumab treatment up to the end of the study.

Treatment-emergent AEs (TEAEs) are defined as AEs occurring after the first dose of IMM-101. Only TEAEs will be presented in summary tables and all AEs (i.e., TEAEs and non-TEAEs) will be listed by patient within cohort.

TEAEs will be summarised by MedDRA system organ class and preferred term using standard incidence and frequency tables. The incidence of TEAEs will be presented as the proportion of patients with at least one AE by system organ class and preferred term and frequency of TEAEs will be calculated as the number of events by system organ class and preferred term.

Treatment-related AEs are defined as AEs which are related to study treatment (IMM-101 and/or nivolumab, and/or ipilimumab if after ipilimumab dosing in cohort B). Related AEs will be those assigned by the investigator as definitely, probably or possibly related to study treatment or with an unknown relationship. Relatedness will be assessed to each of IMM-101, nivolumab and ipilimumab separately as well as for the combined treatment combination. The incidence and frequency of treatment-related AEs, SAEs, and immune-related AEs will be presented, as for all TEAEs.

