For cohort B patients, only TEAEs occurring prior to the start of treatment with IMM-101 + ipilimumab or TEAEs assessed as related (i.e. definitely, probably or possibly related) to nivolumab will be included in the primary safety endpoint evaluations. For the exploratory evaluation of safety, only TEAEs occurring after the start of treatment with IMM-101 + ipilimumab will be included (including any TEAEs related to nivolumab but occurring after the start of ipilimumab).

Grade 3 and above AEs, AEs leading to study withdrawal and AEs leading to death will be summarised by cohort, if present, and listed as above.

The incidence, frequency and severity and type of all TEAEs (following the start of IMM-101 administration, regardless of combination therapy received) will be included in the data presentations, for the combined cohorts.

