2.2 Study Endpoints

2.2.1 Primary Endpoints

The primary efficacy endpoint of the study is the ORR calculated from the BOR of patients as assessed by RECIST 1.1. ORR will be assessed at the end of study or when all patients have withdrawn, if this is sooner. For cohort B, ORR will apply to BOR from tumour assessments during IMM-101 + nivolumab treatment only. ORR and BOR will also be assessed for subgroups based on PD-L1 status (positive or negative/undetermined) in cohort A patients.

The primary safety endpoint of the study is the incidence, frequency and severity of AEs, serious adverse events (SAEs), treatment related AEs, immune-related AEs, Grade 3 and above AEs and AEs leading to IMM-101 discontinuation or study withdrawal experienced during treatment with IMM-101 + nivolumab for both cohorts.

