5.4 Data Presentations

The data will be summarised in tabular form by Cohort apart from disposition of subjects, protocol deviations, background and demographic data (including baseline disease status, medical history, previous melanoma treatment and surgery,

prior/concomitant medications and concomitant surgeries), exposure, compliance and adverse events which will be summarised by Cohort and overall subjects. Cohorts will be labelled 'Cohort A' and 'Cohort B'.

Listings will be sorted by Cohort, subject number and date/time of assessment. Where listings are presented for all subjects, any screening failure subjects will be presented separately from enrolled subjects.

Data will be summarised and listed using the analysis sets as defined in Table 1 of this SAP.

Table 1: Analysis sets used to present summaries and listings

	All Subjects	Enrolled	ITT	SAF
Tables	
 Disposition 		
 Protocol deviations Demography Baseline disease status Compliance Efficacy (repeated on PPS for selected outputs for Cohort A only) 	
 Medical history Previous melanoma treatment/radiotherapy/surgery Prior and concomitant medications Concomitant surgical procedures Exposure Adverse events Injection site reactions Clinical laboratory parameters Vital signs
Listings	
 Completion/withdrawal Eligibility Protocol deviations Analysis sets Informed consent Demography Melanoma diagnosis Visit dates 	
 Time on study and study drug exposure Medical history Previous melanoma treatment/radiotherapy/surgery Prior and concomitant medications Concomitant surgical procedures Baseline, follow-up and new lesions Response assessment Serology sample Pregnancy test PD-L1 biopsy BRAF testing Blood and biopsy samples Vital signs ECG results Physical examination ECOG performance status 	
 Efficacy 	
 Post completion anti-melanoma treatment Administration Adverse events Injection site reactions Clinical laboratory parameters

For safety summaries, only scheduled post-baseline data will be tabulated, post-baseline repeat/unscheduled assessments will be disregarded, although they will be listed and in particular all clinically significant values will be noted.

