5.13 EFFICACY EVALUATION

5.13.1 Primary Endpoint

The primary endpoint will be analysed using the ITT set and repeated for the PPS for Cohort A only.

Primary Analysis

The primary efficacy endpoint of the study is the ORR calculated from the BOR of subjects as assessed by RECIST 1.1.

The investigator response will be entered into the Response Assessment (RECIST 1.1) page of the electronic Case Report Form (eCRF) at each scan assessment to be used in the derivation of BOR.

A confirmed response will be used in the derivation of BOR. A confirmed response is defined as a response obtained from a scan repeated at least 4 weeks following a scan with designation of complete response (CR) or partial response (PR), as defined using Table 3 of RECIST 1.1. In addition, the following approaches will be taken:

- Where a confirmatory assessment is non-evaluable (NE) but the subsequent scan maintains the same response/progression, the response/progression will be considered confirmed (e.g. PR-NE-PR).
- Subjects without a confirmed response of CR or PR will have their next best response (stable disease (SD) or otherwise progressive disease (PD)) assigned as their BOR.
- Subjects without a BOR assessment, such as those with no post-baseline responses or only NE responses, will be assumed to have a BOR of PD using a worst-case approach.

For Cohort A, BOR is defined as the best confirmed response designation, recorded from the first post-baseline scan until and including the last scan on study for each subject.

For Cohort B, BOR is defined as the best confirmed response designation, recorded from the first post-baseline scan until and including the last scan on study for each subject for those receiving IMM-101 and nivolumab, or the last scan performed prior to treatment with ipilimumab. No scan performed once ipilimumab treatment commences will be included.

All scans within these periods, whether scheduled or unscheduled, will be evaluated for overall response.

ORR is calculated as the number of subjects with a BOR of confirmed CR or PR divided by the number of subjects in the analysis set. ORR is calculated for each cohort separately.

Summaries of BOR (best confirmed overall response designation)

The BOR will be summarised for each cohort. The ORR and accompanying exact binomial 95% confidence intervals (CI) will also be presented.

Listings of lesions assessments and BOR

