5.15 SAFETY EVALUATION

5.15.1 Adverse Events

AEs will be coded using the latest MedDRA dictionary version. The version used will be indicated in the data summaries and listings.

A treatment-emergent adverse event (TEAE) is defined as an AE that started on or after the start of the administration of IMM-101. If adverse event dates are incomplete and it is not clear whether the adverse event was treatment-emergent, it will be assumed to be treatment-emergent.

The relationship with each study treatment will be entered in to the eCRF for IMM-101, nivolumab and ipilimumab. A treatment-related TEAE is defined as a TEAE that is possibly, probably or definitely related to the study treatment. For each treatment, where the TEAE has a missing relationship it is assumed to be related to the treatment for analysis purposes.

A summary table will present the following:

- TEAEs (events and subjects).
- Serious TEAEs (events and subjects).
- Treatment-related TEAEs (relating to IMM-101 and/or nivolumab and/or ipilimumab) (events and subjects).
- Immune-related TEAEs (events and subjects).
- TEAEs with a Common Terminology Criteria for Adverse Events (CTCAE) Grade of 3 or above (events and subjects).
- TEAEs leading to discontinuation of IMM-101 (subjects only).

- TEAEs leading to withdrawal from study (subjects only).
- TEAEs leading to death (subjects only).
- TEAEs by CTCAE grade (1 to 5) (subjects only).
- TEAEs by severity (mild/moderate/severe/life threatening/death) (subjects only).
- TEAEs by relationship to study treatment and the pooled study treatment related category (subjects only).

In the above summaries, if a subject experienced more than one TEAE, the subject will be counted once using the most related event for the “by relationship to study treatment” and “related to IMM-101/nivolumab/ipilimumab” summaries, at the worst grade for the “by CTCAE grade” summary, and at the worst severity for the “by severity” summary.

A summary table will also be produced for Cohort B subjects only for AEs which occur at or after the start of infusion of ipilimumab. Any nivolumab related TEAEs occurring after the start of ipilimumab administration will be included. The summary will present the following:

- TEAEs (events and subjects).
- Serious TEAEs (events and subjects).
- Treatment-related TEAEs (relating to IMM-101 and/or ipilimumab) (events and subjects).
- Immune-related TEAEs (events and subjects).

The following tables will be presented:

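### No adverse event table in SAP 5.15.1 delivers the Cohort B primary safety endpoint, which the protocol cuts at the start of ipilimumab

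*SAP*

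**What the plan says.** SAP 2.2.1 defines the primary safety endpoint by treatment period, ending with "AEs leading to IMM-101 discontinuation or study withdrawal experienced during treatment with IMM-101 + nivolumab for both cohorts". Protocol 11.1.3 gives the operating rule: "For cohort B patients, only TEAEs occurring prior to the start of treatment with IMM-101 + ipilimumab or TEAEs assessed as related" to nivolumab enter the primary safety evaluation. The same section sends events after the switch, including late nivolumab-related ones, to the exploratory evaluation. It also plans a separate display of all TEAEs for the combined cohorts, whatever combination was being given.

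SAP 5.15.1 opens with "A treatment-emergent adverse event (TEAE) is defined as an AE that started on or after the start of the administration of IMM-101", and sets no end to that window. It then specifies a main summary table, five tables by system organ class and preferred term or subsets of these (all, by relationship, serious, immune-related, Grade 3 or above), and one period-specific table: "A summary table will also be produced for Cohort B subjects only for AEs which occur at or after the start of infusion of ipilimumab". Under SAP 5.4 the columns come from the rule "exposure, compliance and adverse events which will be summarised by Cohort and overall subjects".

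For response, the SAP does apply the cut. SAP 5.13.1 says of Cohort B: "No scan performed once ipilimumab treatment commences will be included".

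The protocol is not fully consistent. Its primary safety bullet in 11.1.3 describes treatment-related events as "related to IMM-101 and/or nivolumab/ipilimumab (as applicable" and ends with "AEs leading to IMM-101 discontinuation or study withdrawal throughout the study", which reads as unrestricted.

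**The concern.** The SAP states one endpoint and tabulates another. An investigator or reader would take the Cohort B column of the main adverse event tables as the primary safety result for IMM-101 + nivolumab. For any patient who has switched, that column also counts events that began under IMM-101 + ipilimumab.

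The stated purpose (Protocol Section 4, SAP 2.1) is to set the combination's adverse event profile beside published data for nivolumab alone. Ipilimumab-period events in the column confound that comparison. In a purely descriptive trial, the tabulated figure is the result.

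**Working it through.** No figure in the plan needs reproducing. The check compares each table in SAP 5.15.1 with the protocol's rule, then asks whether the endpoint can be recovered from the tables that are planned.

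**Tables against the rule**

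| SAP 5.15.1 output | Events included | Cohort B primary rule applied? |
|---|---|---|
| Main summary (11 rows) | All TEAEs from first IMM-101; the treatment-related row counts ipilimumab-related events | No |
| Five further tables (SOC/PT, relationship, serious, immune-related, Grade 3+) | All TEAEs, no period limit | No |
| Cohort B post-ipilimumab summary (4 rows) | Events at or after first ipilimumab | No; this is the exploratory endpoint |

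The all-TEAE tables match the protocol's combined-cohort display, which is legitimate but is not the primary endpoint. Section 6 of the SAP lists five changes from the protocol. Its only adverse event item concerns who enters the interim safety reviews.

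**Effect per patient**

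Inputs: 8 planned Cohort B patients (SAP Section 3); 5 recruited when recruitment was suspended (SAP Section 4). A patient whose only qualifying events are post-switch and not nivolumab-related is in the SAP table but not in the endpoint.

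- 1/8 = 12.5 percentage points
- 1/5 = 20 percentage points

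**Can the endpoint be recovered by subtraction?**

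For a given row, let M be the Cohort B patients with an event in the main table and P those with one in the post-ipilimumab table. The endpoint counts patients with a pre-switch event or a nivolumab-related post-switch event.

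- The M − P patients who have no post-switch event must have a pre-switch one, so they are always in the endpoint.
- Each of the P patients may or may not be: the tables do not show who also had a pre-switch event or which post-switch events were nivolumab-related.
- Hence M − P ≤ endpoint count ≤ M, and the width is P/8.

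| P (illustrative) | Width with 8 patients |
|---|---|
| 1 | 1/8 = 12.5 points |
| 2 | 2/8 = 25 points |
| 3 | 3/8 = 37.5 points |

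For example, M = 6 and P = 3 leaves the incidence anywhere from 3/8 = 37.5% to 6/8 = 75%.

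For some components there is nothing to subtract. The post-ipilimumab table has no row for Grade 3 or above, IMM-101 discontinuation or study withdrawal, all of which belong to the primary endpoint, and no breakdown by SOC/PT.

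**The case against.** The strongest counter-argument is that the information exists and the cohort is tiny. SAP 5.15.1 requires the adverse event listing to show onset relative to each treatment, with separate listings for serious, immune-related, Grade 3+, discontinuation/withdrawal and fatal events. With at most eight planned patients, the endpoint could be built by hand. That is true, but a primary endpoint assembled by hand from a listing is not a prespecified summary.

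Subtraction also fails less completely than the patient-count bound suggests. The endpoint includes event frequency, and event counts do subtract: main minus post-ipilimumab gives pre-switch events for the all, serious and immune-related rows. This stands, but only for those three rows, and it still omits the late nivolumab-related events. The treatment-related rows do not subtract, because the two tables define them differently.

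The lower bound M − P is an extreme case: none of the P patients would have a qualifying pre-switch event or a nivolumab-related later one. For the any-TEAE row this may be unlikely. The bound shows what the tables leave undetermined; it does not predict the distortion.

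SAP 5.2.8 lists IMM-101 + ipilimumab as a Cohort B subgroup, tabulated only if it reaches 50% of enrolled patients (4 of 8, or 3 of 5). Applied to the post-ipilimumab table, that threshold would remove it when there are fewer switchers, although 5.15.1 says the table will be produced. This needs reconciling, but it leaves fewer split tables, not more.

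Finally, the protocol's unrestricted bullet gives the SAP's main table some support, and the shells (a separate document under SAP Section 1) might contain a restricted table. Neither settles the matter. The specific Cohort B rule follows the general bullet in the same section, SAP 2.2.1 also limits the endpoint to the nivolumab period, and the SAP text should define how its own primary endpoint is tabulated.

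**Conclusion.** The concern holds. SAP 5.15.1 as written reports a different quantity from the primary safety endpoint in SAP 2.2.1 and Protocol 11.1.3 as soon as a switched Cohort B patient has a post-ipilimumab event that is not nivolumab-related. The departure is undeclared. Incidence moves by 12.5 points per affected patient with eight patients, or 20 with five, and the planned tables determine the patient count only to within P/8.

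This assumes that at least one patient switches and that the unseen shells add no restriction. The documents give neither the number of switchers nor the event rates, so the expected size is unknown; with no switchers the tables and the endpoint coincide. Cohort A is untouched and no hypothesis is tested. It should be fixed before the tables are run, but it does not threaten the trial.

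**What to change.** - Add to SAP 5.15.1 a Cohort B primary safety table set: the overall summary plus the SOC/PT, relationship, serious, immune-related and Grade 3+ tables. Include TEAEs with onset before the first ipilimumab infusion, plus nivolumab-related TEAEs after it.
- State that a late nivolumab-related event counts in both the primary and the exploratory tables, as Protocol 11.1.3 implies. State also how unknown or missing relationship and partial onset dates around the switch are handled.
- Keep the post-ipilimumab table and say whether the 50% threshold in SAP 5.2.8 governs it. Keep the all-TEAE combined-cohort display, labelled as covering all events whatever combination was given.
- Reconcile the unrestricted wording of the Protocol 11.1.3 primary safety bullet, and the period wording of SAP 2.2.1, with the Cohort B rule. Record the outcome in SAP Section 6.

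The cost is one filter on adverse event onset date, first ipilimumab date and nivolumab relationship (all already collected), a few small Cohort B tables, and some SAP wording. If the sponsor does prefer the unrestricted tables as primary, the least that is needed is a declared and justified change in SAP Section 6.

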## **5.2.3** Exploratory Endpoints

The following additional exploratory endpoints, will be assessed at the end of the study and are:

- ORR using irRC for both cohort A and cohort B, assessed using BOR by irRC, with the same methods of calculation as for the primary endpoint of ORR (above).
- Duration of Response and Time to Response for both cohort A and cohort B, assessed by RECIST 1.1. For any patients in cohort B who change treatment on study to IMM-101 + ipilimumab, only responses evaluated until the point of this change in therapy are included.
- Disease Control, assessed for patients in cohort B of the study only, and defined as those patients with a response (CR or PR) or SD based on RECIST 1.1. and assessed at each scan assessment point from Week 14 onwards. Disease Control is evaluated for treatment with IMM-101 + nivolumab only and for any patients who change treatment to IMM-101 + ipilimumab, disease control is assessed until and including the last evaluable tumour assessment prior to the change in therapy.

- For the subgroup of patients in cohort B who receive IMM-101 + ipilimumab as subsequent treatment: the incidence, frequency and severity of adverse events, serious adverse events, treatment-related adverse events and immune-related adverse events (as listed in the SmPC for ipilimumab) experienced following the start of ipilimumab treatment up to the end of the study.
- To evaluate BOR for cohort B to include any responses obtained following a change in therapy from IMM-101 + nivolumab to IMM-101 + ipilimumab. All tumour assessments on study are included in this evaluation.
- Immunological markers from blood and biopsy samples from both cohorts A and B (to be reported separately to other endpoints).

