2.2.3 Exploratory Endpoints

The exploratory efficacy endpoints of the study are:

- ORR using irRC in patients in both cohort A and cohort B receiving IMM-101 + nivolumab.
- Duration of Response and Time to Response for both cohort A and cohort B receiving IMM-101 + nivolumab and assessed by RECIST 1.1.
- Disease Control, for patients in cohort B of the study only and defined as those patients with a response of stable disease based on RECIST 1.1, assessed at each scan assessment point from Week 14 onwards.
- BOR for cohort B to include any responses obtained following a change in therapy from IMM-101 + nivolumab to IMM-101 + ipilimumab.
- Immunological markers from blood and biopsy samples (to be reported separately to other endpoints).

The exploratory safety endpoint of the study is for any patients in cohort B of the study who took IMM-101 + ipilimumab as subsequent treatment. The incidence, frequency and severity of AEs, SAEs, treatment related AEs, and immune-related AEs from the start of treatment with ipilimumab will be examined.

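### The SAP's adverse event table for the ipilimumab period has no severity row and leaves nivolumab out of its treatment-related row, so it does not match the endpoint it serves

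*SAP*

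**What the plan says.** The exploratory safety endpoint concerns cohort B patients who change to IMM-101 + ipilimumab. SAP 2.2.3 states it as: "The incidence, frequency and severity of AEs, SAEs, treatment related AEs, and immune-related AEs from the start of treatment with ipilimumab will be examined". Protocol 5.2.3 asks for "the incidence, frequency and severity of adverse events, serious adverse events, treatment-related adverse events and immune-related adverse events", and protocol 11.1.3 repeats this in its list of exploratory safety endpoints.

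For relatedness, protocol 11.1.3 says: "Treatment-related AEs are defined as AEs which are related to study treatment (IMM-101 and/or nivolumab, and/or ipilimumab if after ipilimumab dosing in cohort B". The same section limits the exploratory evaluation to TEAEs after the change of therapy, "including any TEAEs related to nivolumab but occurring after the start of ipilimumab".

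SAP 5.15.1 implements the endpoint with a single table: "A summary table will also be produced for Cohort B subjects only for AEs which occur at or after the start of infusion of ipilimumab". Its lead-in says that nivolumab-related events arising in this period are included. Four rows follow, each giving events and subjects: all TEAEs, serious TEAEs, "Treatment-related TEAEs (relating to IMM-101 and/or ipilimumab) (events and subjects", and immune-related TEAEs.

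**The concern.** The table differs from its endpoint in two ways. Severity is part of the endpoint, and nothing in the table reports it. The related row also uses a narrower set of drugs than the protocol's definition and than the related row of the main adverse event table in the same SAP section. Neither departure is listed in SAP section 6.

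Protocol 7.6.2 allows ipilimumab to begin 2 weeks after the last nivolumab dose, so events that an investigator attributes to nivolumab can start inside this window. What is at stake is whether the one summary written for this endpoint gives the related incidence as the protocol defines it, and whether it shows how severe the events were.

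**Working it through.** The plan states no figure for this point, so there is none to reproduce. The check sets the endpoint beside the table and then sizes the effect.

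**1. Severity.**

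| Endpoint element | Ipilimumab-period table | Main adverse event table |
|---|---|---|
| Incidence (subjects) | all 4 rows | yes |
| Frequency (events) | all 4 rows | yes |
| Grade or severity | 0 rows | 3 rows: Grade 3 or above, CTCAE grade 1 to 5, severity category |

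The main table cannot stand in for the missing rows. It is not split at the start of ipilimumab, and its by-grade row counts each subject once at the worst grade. A patient with a Grade 3 event before the switch and another after it appears once, with no indication of period. The Grade 3 or above table by system organ class and preferred term states no restriction to the period either.

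**2. Drugs counted as related.**
- Protocol 11.1.3 definition: "IMM-101 and/or nivolumab, and/or ipilimumab if after ipilimumab dosing in cohort B", which is 3 drugs.
- Related row of the SAP main table: 3 drugs.
- Related row of the ipilimumab-period table: 2 drugs.

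Take an event that starts after ipilimumab and is judged possibly related to nivolumab and not related to the other two drugs. It is counted in the period's TEAE row, and in the serious or immune-related row if it qualifies. It is not counted in the period's related row. It is counted as related in the main table, and under nivolumab in the table by relationship.

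**3. Declared changes.** SAP section 6 has five items: interim cohort size, interim data cut-off, per-protocol definition, per-protocol tables for cohort A only, and subgroup thresholds. None concerns this table. Protocol 11.6 asks for departures to be documented and justified.

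**4. Size.** Inputs:
- Cohort B is planned at 8 (protocol 11.2, SAP section 3).
- SAP 5.2.8 names the IMM-101 + ipilimumab subgroup. It requires at least 50% of enrolled cohort B subjects and fewer than the whole cohort B ITT set.
- SAP 5.1 bases adverse event percentages on the analysis set or a subgroup of it.

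Lower limit for a table: 0.50 × 8 = 4. Upper limit: 8 − 1 = 7. With switchers as the denominator, one patient whose only related event is nivolumab-only moves related incidence by 100/n points:

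| Switchers n | 100/n |
|---|---|
| 4 | 25.0 |
| 5 | 20.0 |
| 6 | 16.7 |
| 7 | 14.3 |

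Example at n = 4: 3/4 = 75% becomes 2/4 = 50%. If all 8 cohort B patients were the denominator instead, the shift would be 100/8 = 12.5 points whatever the number of switchers.

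**The case against.** The case for leaving the table alone has several parts.

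- **The objective is the IMM-101 + ipilimumab combination.** A row limited to those two drugs describes it, and another phrase in protocol 11.1.3 attaches the words as applicable to the nivolumab/ipilimumab part of relatedness. This stands as a reason to show a two-drug count. It does not make that count the protocol's treatment-related category, which adds ipilimumab after the switch without removing nivolumab.
- **Few events would leave the row.** An event drops out only if judged not related to both IMM-101 and ipilimumab. Protocol 9.2.3 sets a high bar for not related, and SAP 5.15.1 treats a missing relationship as related. This stands, and it makes the shifts above per-patient illustrations rather than expected values.
- **The protocol is not uniform on severity.** Sections 9.1 and 11.7.2 mention only incidence and frequency for these patients. True, but the endpoint definitions in the protocol synopsis, 5.2.3 and 11.1.3, and in SAP 2.2.3, all include severity.
- **Listings carry the data.** SAP 5.15.1 lists every event with onset relative to each treatment, and lists Grade 3 or above events separately. With so few patients, grades for the period can be rebuilt by hand. This limits the harm, but a listing is not a summary of the endpoint.
- **The table shells are a separate document that was not available.** They may contain more rows. The SAP text would still need to agree with them.

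A reader might infer that nivolumab toxicity after the switch disappears from the report, that related toxicity over the whole treatment sequence is understated, or that grade is tabulated nowhere. The documents support none of these. Such events stay in the period's TEAE row and count as related in the main table, and grade is tabulated there without a period split.

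**Conclusion.** The mismatch is real on both counts, and its reach is small. The table written for the exploratory safety endpoint leaves the severity part unsummarised and yields a related count that contradicts the protocol's definition. It affects one descriptive table in an optional subset of a planned 8 patients; no primary endpoint or decision rule depends on it.

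The size depends on an assumed number of switchers, on switchers being the denominator, and on SAP 5.2.8 governing this table, which SAP 5.15.1 does not restate. On those assumptions, one nivolumab-only patient moves the related incidence by between about 14 points (7 switchers) and 25 points (4 switchers). A scenario in which all 8 switch should not be used to size the effect, because SAP 5.2.8 would then produce no subgroup table. With fewer than 4 switchers, listings are the planned vehicle.

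**What to change.** In the ipilimumab-period table of SAP 5.15.1:

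- Define the related row as IMM-101 and/or nivolumab and/or ipilimumab, with a sub-row for IMM-101 and/or ipilimumab to describe the current combination. Alternatively, keep the narrower row, label it as such, and declare and justify it in SAP section 6.
- Add rows for TEAEs by worst CTCAE grade and for TEAEs of Grade 3 or above, both restricted to onset from the start of ipilimumab.
- Bring the table shell into line with the text.

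The cost is two or three rows in one table. No new data are needed: relationship to each drug is entered in the eCRF (SAP 5.15.1) and every adverse event is graded (protocol 9.7). The edit should be made before database lock.
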